Appendix A: Recruitment text

This is a study exploring the interaction between diet and cognitive function. If you wish to take part, you will attend a screening session at the university of Liverpool (Eleanor Rathbone building) where you will complete a medical history questionnaire and have your height and weight measured.

If you are eligible, you will be asked to come into the lab (Eleanor Rathbone building, University of Liverpool) for three consecutive weeks for lunch and dinner. Before and after each meal you will be asked to complete a cognitive task.

The lunch provided will be three variations of loaded fries (with beef chilli). You will be asked to serve yourself the amount you would like to eat.

After lunch, you will be given a snack box to eat throughout the day if you wish, and when you return in the evening, you will be given a three-cheese pasta for dinner, followed by a dessert of chocolate brownies.

Following three days of testing you will complete a number of questionnaires.

If you would like to take part, please make sure:

- You currently reside in or around Liverpool and are able to travel to the university for a screening session and lunch and evening meals one day a week for three consecutive weeks.
- You like the foods on offer for lunch and dinner.
- You are 18 years or older
- You are not taking any medication that affects your appetite
- You are a fluent English speaker
- You are not pregnant or breastfeeding
- You are a non-smoker
- You are not partaking in a fast or other restrictive eating for religious reasons at the time of participation
- You have none of the following dietary restrictions:
 - Vegetarian/vegan
 - Gluten-free
 - Dairy-free
 - Sugar-free
 - Any food allergies

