We aim to follow up on this previous study, by covertly manipulating the level of energy density of a meal, using the same parameters as the prior study. In this previous study the foods provided were noticeably different to participants, and so underlying preferences and differences in sensory and nutritional aspects of the meals may have influenced the amount consumed. Equally, this study did not measure whether later intake differed following consumption of desserts varying in energy density. For the present study, the foods provided will be variations on the same meal (loaded fries), so participant's expectations of the meals should be comparable. This will help us to understand whether reformulation to approximately 2kcal/g would lead to a reduction in energy intake, or if further reduction, below 1.5kcal/g is required to influence immediate eating behaviour positively by reducing energy intake. Additionally, if there are significant effects of energy density, it is vital to determine whether these changes are compensated for by consumers later on in the day.

Primary objectives: To observe differences in consumption (g/kcal) when participants are given a meal covertly manipulated to be low, medium or high in energy density.

Secondary objective: To measure later food intake, in order to observe any evidence of later compensation in response to experimental condition.

To measure intake over the full day, in order to understand whether one manipulated meal impacts daily energy intake.

Study Information

Hypotheses:

Based on Flynn et al(18), it is hypothesised that as the energy density of the lunch meal increases from low ED to medium ED, the amount of the lunch consumed (g) will remain similar, but due to the increased energy density, the calories consumed will increase.

As energy density of the lunch meal increases from medium ED to high ED, the amount of lunch consumed (g) will decrease, due to people compensating for the increase in energy density (i.e., participants will attend to satiety signals and adjust meal size).

Design Plan

Study type: Experiment - A researcher randomly assigns treatments to study subjects, this includes field or lab experiments. This is also known as an intervention experiment and includes randomized controlled trials.

Blinding: For studies that involve human subjects, they will not know the treatment group to which they have been assigned.

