Is there any additional blinding in this study? To attempt to reduce the likelihood of aim guessing, participants will be recruited to a study labelled as 'a study of diet on cognitive function'.

Study design: An experimental, within-subjects design. Participants will be asked to visit the lab for three consecutive weeks to complete some questionnaires and eat meals at lunch time and dinner time. Participants will complete all three conditions – low energy density, medium energy density and high energy density meals which will be eaten ad-libitum. Participants will be provided with a box of snacks to eat throughout the day if they wish to, and will return to the lab for dinner, where they will be served an ad-libitum meal and a dessert.

Randomization: Participants will complete all three conditions. The order the conditions are presented to participants will be randomised prior to arrival.

Sampling Plan

Existing Data: Registration prior to creation of data

Explanation of existing data: N/A

Data collection procedures: Participant database. If required, participants will also be recruited from the local community (e.g. adverts on social media/posters in the university)

Inclusion criteria:

- Currently reside in the UK
- Over the age of 18 years
- Fluent English speaker
- Like the test foods
- Have a BMI between the ranges of 18.5 and 35.

Exclusion criteria:

- Pregnant/breastfeeding
- Partaking in a fast or other restrictive eating for religious reasons at time of participation

- Currently following a diet
- On medication that affects appetite
- Being a smoker
- Current or historic eating disorder
- Dietary restrictions/intolerances including:
 - Any allergies
 - Vegan/vegetarian
 - Gluten-free
 - Dairy-free
 - Sugar-free

Procedure:

Once signed up, participants will attend a short screening session, where they will be asked to complete a medical history questionnaire, a baseline demographic questionnaire, have their height and weight measured, and check they like the test foods on offer.

Participants will be told upon registration that they should have the same breakfast the morning of each session. Arrangements will be made for the participants to arrive at the lab around the time they would usually eat their lunch (11.30-2.30) and be allocated to one of the following groups for each session (order randomised):

- Low energy density lunch
- Medium energy density lunch
- High energy density lunch

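### The recruitment text announces that lunch will come in three versions, which cues participants to compare meals whose manipulation is meant to be covert

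*Combined protocol and SAP*

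**What the plan says.** All references are to the combined protocol and SAP.

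- **Primary objectives:** "To observe differences in consumption (g/kcal) when participants are given a meal covertly manipulated to be low, medium or high in energy density".
- **Background, paragraph before the objectives:** the earlier dessert study is criticised because its foods were visibly different, so preferences and sensory differences may have affected the amount eaten. The remedy here is that "the foods provided will be variations on the same meal (loaded fries), so participant's expectations of the meals should be comparable".
- **Design Plan, Blinding:** of participants, "they will not know the treatment group to which they have been assigned". The entry on additional blinding adds a cover story against aim guessing: "participants will be recruited to a study labelled as 'a study of diet on cognitive function".
- **Appendix A, Recruitment text:** it opens with the cover story and then states "The lunch provided will be three variations of loaded fries (with beef chilli". The next sentence says that participants choose how much to serve themselves. Dinner is given as one pasta dish followed by brownies.
- **Data collection procedures and Study flow (Recruitment row):** Appendix A is tied to people who could not join a previous study. Community adverts may be added if needed, and their text is not given.
- **Aim guessing and Analysis Plan:** awareness of the aim is coded from an open question at the last visit. Results are reported with and without aware participants, and also by whether participants identified the ED differences correctly.

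**The concern.** The plan uses one dish because "expectations of the meals should be comparable". A participant who has read that there will be three versions arrives expecting the lunches to differ. From the contrast with dinner, that participant can also infer that lunch is what changes from week to week.

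What is at stake is the interpretation of the primary gram outcome. The second hypothesis predicts fewer grams at high ED than at medium ED and attributes this to people responding to satiety. Someone prompted to look for differences may instead compare the meal with a remembered one, judge it richer, and deliberately take less. Both routes lower grams at high ED, and the primary ANOVA on grams cannot separate them.

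**Working it through.** No figure in the documents settles this point, so the check is a comparison of passages. A short calculation follows on what the planned exclusion analysis would cost.

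**1. What is meant to be hidden, and what Appendix A discloses**

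| Item | Plan's intention | Appendix A |
|---|---|---|
| Study aim (ED and intake) | Hidden by the cover story until debriefing | Still hidden; cover story repeated |
| Which ED is served at a visit | Unknown to participants (Blinding; Sample size) | Not disclosed |
| That ED, calories or healthiness differs | Covert (Primary objectives) | Not mentioned |
| That the lunches differ at all | Expectations should be alike (Background) | **Disclosed before the first visit** |

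Only the last row conflicts. The conflict is with the comparable-expectations rationale. It weakens the covert manipulation without revealing it.

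**2. Could the cue affect the contrast between conditions?** All participants eat all three meals in randomised order, so a cue that shifts intake equally at every meal cancels out. Deliberate comparison need not cancel. It depends on which version is on the plate, and randomising the order does not remove a response that depends on the meal itself.

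**3. Do the planned checks cover it?**
- Awareness is coded only if a participant guesses that the study concerns ED or healthiness and intake. Someone who believes the cognition story but still compares lunches is coded as unaware.
- The ranking check is described inconsistently. The Aim guessing section and the Study flow table ask for a ranking by energy density; the Procedure and Appendix H ask for healthiness.
- Both checks come after the final dinner, so they can describe awareness but cannot prevent the prompt.

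**4. Cost of excluding aware participants (illustration only).** Inputs from Sample size: d = 0.52, N = 32, and power printed as 0.8%, read as 80%. Alpha is 0.05 from Inference criteria; two-sided is assumed.

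For the paired t-test, the noncentrality is d × √n with n − 1 degrees of freedom. At n = 32 it is 0.52 × √32 = 2.94 and power is 81.3%, so the plan's 32 reproduces.

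For the repeated-measures ANOVA, λ = n × 3 × f² / (1 − ρ) with f = 0.25. Sphericity and ρ = 0.5 are assumed, since the plan states no correlation. This gives λ = 0.375 × n.

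| Excluded | n | d√n | Paired t-test power | λ | ANOVA power |
|---|---|---|---|---|---|
| 0 | 32 | 2.94 | 81.3% | 12.0 | 86.6% |
| 4 | 28 | 2.75 | 75.6% | 10.5 | 81.2% |
| 8 | 24 | 2.55 | 68.4% | 9.0 | 74.1% |
| 12 | 20 | 2.33 | 59.8% | 7.5 | 65.1% |

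The documents give no awareness rate, so the excluded counts are assumptions. The table shows what the excluded run would lose. It does not show how many aware participants the sentence would add.

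**The case against.** A reader might infer that the sentence gives away the covert manipulation to every participant. The documents do not support that.

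- **The manipulation is not given away.** Appendix A says nothing about energy density, calories, healthiness or an interest in intake. A study of diet and cognition could plausibly vary the lunch, so the sentence even fits the cover story. Participants who notice unexplained differences might otherwise look for a reason. This stands, and it limits the point to a cue.
- **Universal exposure is not shown.** Appendix A is linked to one recruitment route and the text of other adverts is not given. The information sheet (Appendix C) is not in the text available here, so whether it repeats or softens the wording is unknown. This stands too.
- **Participants may notice anyway.** Table 1 gives mince of 250, 313 and 769 g, carrot of 100, 52 and 6 g, and moisture of 76.1, 70.2 and 47.2 per 100 g across low, medium and high ED. They also rate each lunch on sensory scales. The added effect of the sentence may therefore be small. That is a fair limit on its importance, but it is no reason to add a prompt.
- **The plan monitors awareness.** It does, and the full-sample result is always reported, so exclusion costs power only in the secondary run. Monitoring still does not prevent the cue, and it misses participants who compare meals without guessing the aim.

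It is also tempting to cite the two of three lunches eaten after an earlier version as a measure of the problem. That fraction would be the same in any three-period crossover and says nothing about the effect of the wording.

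**Conclusion.** The point holds as a modest, inexpensive improvement. Those who read Appendix A are told in advance that the lunches will differ. This sits uneasily with the comparable expectations in the Background and leaves a rival explanation for reduced grams at high ED. It is a risk of expectation or demand effects, not a demonstrated bias, and its size cannot be computed from the documents.

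The conclusion rests on two assumptions: that at least some participants are recruited with Appendix A as written, and that knowing the meals differ makes comparison more likely than noticing unprompted. It does not require that anyone learns that ED is the factor varied.

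**What to change.** In Appendix A, replace the sentence with: *The lunch provided will be loaded fries (with beef chilli).* Use the same neutral wording in any other material that participants see before debriefing, including community adverts and the information sheet. Leave the disclosure that the meals differed to the debriefing text (Appendix I), which already gives it.

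The cost is one sentence and a minor ethics amendment. Slightly more is withheld until debriefing, in a study that already uses a cover story and a full debrief. Dietary screening should be unaffected: the dish and the beef are still named, and Table 1 lists the same chilli ingredients for all three recipes, in different amounts. The edit will not stop participants from noticing differences for themselves, so the aim-guessing and ranking analyses should stay.

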Appendix B: Baseline questionnaire

1. Gender

- Male
- Female
- Other

2. Age:

3. Ethnicity:

- White English/Welsh/Scottish/Northern Irish/British
- White Irish
- Any other White background
- White and Black Caribbean
- White and Black African
- Any other mixed/multiple ethnic background please describe
- Indian
- Pakistani
- Bangladeshi
- Chinese
- Other Asian
- African
- Caribbean
- Arab
- Any other ethnic group

4. What is your highest educational qualification?

- Less than high school
- High school completion
- College or foundation degree
- Bachelor's degree
- Master's degree
- Doctoral or professional degree

5. This is an attention check. How many times have you visited the planet Mars?

- Several times
- Just once
- Never

Think of a ladder (see image) as representing where people stand in society. At the top of the ladder are the people who are best off—those who have the most money, most education and the best jobs. At the bottom are the people who are worst off—who have the least money, least education and the worst jobs or no job. The higher up you are on this ladder, the closer you are to people at the very top and the lower you are, the closer you are to the bottom. Where would you place yourself on the ladder?

6. Choose the number whose position best represents where you would be on this ladder:

7: Please state the highest educational attainment of your primary caregiver(s) when you were aged 8-10.

1 = less than high school

2 = high school

3 = 2-year degree

4 = 3/4-year degree

5 = master's degree

6 = doctorate/professional degree

Primary caregiver 1 _____

Primary caregiver 2 _____

8: Please state the occupation of your primary caregiver(s) when you were aged 8-10.

Primary caregiver 1 _____

Primary caregiver 2 _____

Appendix E: Sensory ratings:

Please rate the meal you just had on the following scales:

Pleasant

Sweet

Salty

Savoury

Appetising (visually)

Familiar

Filling

Soft

Appendix F: Satiety responsiveness

		Strongly disagree 1	Disagree 2	Neither agree nor disagree 3	Agree 4	Strongly agree 5
1.	I often leave food on my plate at the end of a meal.					
2.	I often get full before my meal is finished.					
3.	I get full up easily.					
4.	I cannot eat a meal if I have had a snack just before.					

Appendix G: Compensatory Health Beliefs

		Strongly disagree 1	Disagree 2	Neither agree nor disagree 3	Agree 4	Strongly agree 5
1.	To maintain your weight, it is fine to do less exercise if you eat small portions					
2.	To maintain your weight, it is fine to have less exercise if you eat products with a front-of-package logo					
3.	When I eat less, it's not necessary to have a lot of exercise					
4.	When I mainly eat products with a front-of-package logo, it is not necessary to have a lot of exercise					
5.	If I eat a small meal, it's fine to have a larger portion during the next meal					
6.	To maintain your weight, it is fine to eat a large meal, if you eat a small portion during the next meal					
7.	To maintain your weight, it is fine to eat a high caloric snack in between meals, if you compensate for this by eating a smaller portion later in the day					
8.	If I eat a small meal, there is no harm in eating more cookies and candies					

Appendix H: Follow up questions

1. What do you think the aim of this study was?

2. Can you please rate the lunches you have been given in order of healthiness: i.e. write week 1, week 2, week 3 in the spaces below.

- a. _____ (healthiest)
- b. _____
- c. _____ (least healthy)

Appendix I: Debriefing text

In this study we were interested in the effect of energy density (measured by calories per gram of food) on consumption – where the energy density of the loaded fries was different each week. Energy density was altered by changing the ingredients (i.e. 20% fat beef mince/15% fat beef mince/5% fat beef mince) or the proportions of ingredients (i.e. a greater proportion of vegetables). All participants were presented with the same three meals, each in a random order.

We wanted to investigate whether people compensate when given a less healthy food option by eating a smaller amount compared to when they are given less unhealthy options. Additionally, we wanted to see if people compensate later in the day, by eating a smaller portion for dinner when they had a less healthy meal at lunch.

We hypothesised that individuals would compensate more for the least healthy option by eating less (whether at lunch time or dinner time).

The questionnaire about satiety responsiveness and compensatory health beliefs will be used to test any characteristics and motivations that may impact the amount of food eaten.

If this study has raised any issues regarding your weight or eating behaviours, we recommend contacting your doctor.

The following NHS page provides information and guidance on eating a healthy, balanced diet:
<https://www.nhs.uk/live-well/eat-well/>

Thank you very much for your participation in our study.

References

2. Lin B-H, Guthrie JF. Nutritional quality of food prepared at home and away from home, 1977-2008. US; 2012.
5. Public Health England. Calorie reduction: The scope and ambition for action. UK: PHE; 2018.
